**Background:**

Postpartum haemorrhage (PPH) is a significant factor in maternal morbidity and mortality worldwide with uterine atony the commonest cause of PPH. In 2009, the Society of Obstetricians and Gynecologists of Canada (SOGC) recommended the use of an intravenous (IV) carbetocin bolus, instead of a continuous oxytocin infusion in elective Cesarean delivery for the prevention of PPH from uterine atony(1).

Carbetocin (1-deamino-1-carba-2-tyrosine (0-methyl)- oxytocin) is a synthetic analogue of human oxytocin and has a similar mechanism of action. The peak onset of action is 2 minutes, with a 60-minute duration of action following IV bolus. The dose recommended by the SOGC is 100mcg. However, recent studies have suggested that a 10-100mcg dose following low risk Cesarean delivery under spinal anesthesia can produce satisfactory uterine tone (2)(3). Carbetocin is currently used routinely at British Columbia Women's Hospital (BCWH) as a first-line pharmacological intervention at a dose of 50mcg or 100mcg during elective and emergency Cesarean deliveries. The range in dosing at BCWH stems from contemporary studies showing different effective dose 90 (ED90) doses. Khan et al showed that the ED90 dose producing satisfactory uterine contraction in women undergoing low risk elective Cesarean delivery was 14.8mcg(3). Nguyen-Lu et al showed a higher ED90 of 121mcg for women undergoing emergency Cesarean delivery after at least 3 hours of an oxytocin infusion in labour. They concluded that a 121mcg

dose could be an underestimation for this group of patients, but to use higher than the currently recommended doses with caution due to increased risk of arrhythmia(4).

A recent study involving 20 women undergoing Cesarean delivery suggested that carbetocin 100mcg IV bolus may be associated with prolongation of the QTc interval on the electrocardiogram (ECG)(5). They advocate that carbetocin should not be used in patients with prolonged QTc or LQTS. This issue has not been rigorously investigated, and the possibility of harm in patients with comorbid cardiac conditions remains unclear. Pregnant patients with pre-existing prolonged corrected QT (QTc) interval (drug induced) or congenital long QT syndromes (LQTS) are at significant risk for a cardiac event, especially during the post-partum period.

QTc interval prolongation is associated but not the cause of torsades de pointes (TdP)(6), a polymorphic ventricular tachycardia which can lead to cardiac arrest. QTc interval has been shown to be a poor predictor of the risk of TdP. Prior studies have demonstrated a more reliable predictor of risk of TdP is the interval between the peak and the end of the ECG T-wave (Tp-e), which is a surface ECG marker of dispersion of repolarization (TDR) across the myocardial wall(7)(8). Normal TDR reflects the way that different layers of the myocardial wall repolarize at different rates – the outside fastest, then the inside and finally the middle. It has been shown that exaggeration of TDR provides the right environment and trigger for TdP. This surface ECG marker can be used as a tool to assess the risk posed by a drug that prolongs the QT interval(9). The current evidence shows that, if TDR is not increased, the risk of TdP is not increased, even if the QT interval is prolonged. Conversely, if TDR is exaggerated, the risk of TdP is raised, even if the absolute QT interval is within normal limits.

The normal values for QTc and Tp-e are different in pregnancy. This has been elucidated by Tanindi et al who found that QTc, Tp-e and Tp-e/QT ratio were all increased in the third trimester of pregnancy but were still within the normal range of non-pregnant women(10).

Every patient undergoing Cesarean delivery must receive a uterotonic agent to prevent uterine atony. Currently carbetocin is the first line treatment including for those patients with LQTS. There is no clear evidence currently whether carbetocin is safe in these patients and whether there is a dose dependant effect on myocardial repolarisation. The alternative treatments to carbetocin used as 2nd and 3rd line agents include oxytocin, misoprostol, ergometrine and hemabate. Oxytocin poses a risk of prolonging the QTc and the Tp-e after a bolus dose of 5Units over 1 minute (11), although some data suggests the average prolongation may not be more than 40ms (+/- 20ms), in patients receiving 10Unit IV boluses(12). A reduced dose of oxytocin, 5Units per 1,000mL lactated ringers has been shown to not prolong the QT interval, while still effectively decreasing post-partum haemorrhage(12). However, a couple of case reports describe the use of oxytocin for induction of labour and to aid uterine contraction in women with LQTS without any effect. The current recommendation is to use oxytocin with caution in patients at increased risk of or with LQTS. There is no information on the effects of misoprostol, ergometrine or hemabate on QTc interval or repolarization dynamics. It is therefore important to carry out this study to determine the safe use of carbetocin in patients at risk of prolonged QT interval or with LQTS.

To date no study has explored the effect of carbetocin dose on TDR in pregnant patients. Therefore, this study aims to examine in detail the relationship between carbetocin dose and TDR in healthy women having Cesarean delivery under spinal anaesthesia.

#### **Study design and methodology:**

This will be a prospective, randomized, double blind study in healthy women undergoing Cesarean delivery. It will examine the effect of carbetocin dose on TDR using 50mcg and 100mcg intravenous boluses.

Arm 1: Intravenous injection of Carbetocin 50mcg (C50) + 0.9% Sodium Chloride (total volume 10 mL) over 1 minute.

Arm 2: Intravenous injection of Carbetocin 100mcg (C100) + 0.9% Sodium Chloride (total volume 10 mL) over 1 minute.

#### **Hypothesis:**

We hypothesize that carbetocin increases indices of myocardial repolarization (Tp-e and QTc) with a dose-dependent relationship following Cesarean delivery under spinal anesthesia.

#### **Primary outcome:**

1. Change in Tp-e from baseline to 5 mins post carbetocin

#### **Secondary outcomes:**

1. Change in QTc from baseline to 5 mins post carbetocin within and between groups (50mcg vs. 100mcg)
2. Changes in Tp-e and QTc between groups (50mcg vs. 100mcg) from baseline to 5 minutes and 10 minutes post carbetocin
3. Changes in Tp-e and QTc within and between groups (50mcg vs. 100mcg) from post spinal to 10 mins post carbetocin
4. The presence of atrial and ventricular arrhythmias within and between groups (50mcg vs. 100mcg)

#### **Inclusion criteria:**

- Pregnant patients  $\geq$  36 weeks gestation, for elective Cesarean delivery under single-shot spinal anesthesia
- American Society of Anesthesiologists (ASA) class 2
- Patients  $\geq$  19 years of age

#### **Exclusion criteria:**

- Long QT syndrome
- Cardiac disease or rhythm abnormalities
- Family history of long QT syndrome or abnormal cardiac conduction
- Currently taking medication that is known to prolong the QT interval (appendix 5(13))

- Women who are high risk for uterine atony as outlined in SOGC (History of PPH, Preeclampsia, hereditary coagulopathies, fetal death, polyhydramnios, multiple gestation, macrosomia, high parity, maternal fever, prolonged ruptured of membranes, fibroid uterus, abnormal placentation, induction of labor, uterine anomalies)(14)
- Known allergic reaction or hypersensitivity to carbetocin or any other oxytocin homologue
- Patients who are unable to give informed consent because of a language barrier as the study team only speaks English and will be unable to complete consent process and study procedure appropriately.

**Withdrawal criteria:**

- Post-partum haemorrhage requiring second-line uterotonic use
- Withdrawal of consent at any time

**Recruitment:**

Patients having an elective Cesarean delivery typically arrive 60-90 minutes prior to scheduled procedure. Upon arrival, patients check in at the admitting desk where the admitting nurse will provide eligible patients with a Patient Information Sheet (Appendix 1) describing the study. The patients and her support persons are brought to the pre-operative waiting area before their procedure. After about 30 minutes and once the patient has had a chance to read the information sheet, one of the study team members will approach the patients and fully explain the details of the study (i.e., why the study is being carried out and how it will affect her care if she chooses to participate) and answer any questions. The patients will also be shown the ECG machine and ECG leads which will be used if she chooses to participate. We will leave her with the consent form to further read about the study and discuss it with her support persons. Approximately 30 minutes prior to elective Cesarean delivery, we will ask the nurse what the patient has decided. If the patient agrees, one of the study team members will formally go through the consent process with the patient, obtaining informed written consent (Patient Consent Form in appendix 2).

We will not attempt to consent patients in the proceeding days before the surgery as this would often require an extra hospital visit and thus place burden on the patients' time. However, we will provide the Patient Information Sheet and Informed Consent Form to all women once the decision for a Cesarean delivery has been made. The decision usually occurs in the obstetric care provider's office where the patient is given an information pack detailing their Cesarean delivery. This information pack is compiled by the admissions team at BCWH, and they have agreed to allow study investigators to add their Patient Information Sheets and Informed Consent Forms to the packs sent out to obstetric care providers. The Patient Information Poster (appendix 3) will also be e-mailed to all obstetric offices to print and display on their notice boards. Finally, the information poster will also be placed in the operating room admissions area and research notice boards around the hospital, with the aim that patients will recognize the study when they come in for their elective Cesarean delivery.

Investigators will educate anesthesiologists, surgeons and operating room nursing staff about the study directly through departmental rounds and by e-mail.

All study procedures will take place in the pre-operative area and operating room at BCWH. These will be conducted by one of the study team members; however, the study team will not then be involved with the participant's ongoing elective Cesarean delivery.

#### **Randomization:**

Microsoft Excel 2010 will be used to generate a randomization sequence that will be used to allocate participants to either Carbetocin 50mcg (C50) or Carbetocin 100mcg (C100). Allocation will be concealed using sequentially numbered opaque envelopes.

[figure not shown]
#### **Blinding:**

The ECG reviewer will be blinded to the study group and the status of the ECG recording (pre- or intra-operative). Each ECG will be given a random three-figure code to allow identification of the paired pre and intra-operative traces after analysis.

[figure not shown]
The ECG reviewer will not be involved in the recruitment or randomization of the patients, or in the conduct of the anesthesia or acquisition of the ECG recordings, all of which will be performed by one of the study team members.

#### **Interventions (Study Protocol):**

After obtaining written informed consent, enrolled patients will be randomized to one of two groups (C 50 or C100). Block randomization will be prepared using computer generated random numbers. Allocation

V1 - Fourth intercostal space on the right sternum  
V2 - Fourth intercostal space at the left sternum  
V3 - Midway between placement of V2 and V4  
V4 - Fifth intercostal space at the midclavicular line  
V5 - Anterior axillary line on the same horizontal level as V4  
V6 - Mid-axillary line on the same horizontal level as V4 and V5  
a)

RA (Right Arm) - Anywhere between the right shoulder and right elbow  
RL (Right Leg) - Anywhere below the right torso and above the right ankle  
LA (Left Arm) - Anywhere between the left shoulder and the left elbow  
LL (Left Leg) - Anywhere below the left torso and above the left ankle  
b)

will be concealed using sealed sequentially numbered opaque envelopes. In the pre-operative area ECG electrodes will be sited at standardized locations (figure 1) for acquisition of a pre-operative 12 lead ECG in the supine position – this will be the baseline ECG.

Participants' baseline ECGs will be analysed by the study team in the preoperative area. If the QT interval is prolonged on the baseline ECG, the patient will be withdrawn from the study and an obstetric internal medicine specialist will be consulted. The ongoing care will then be determined by the attending obstetric, anesthetic and obstetric internal medicine physicians. . The QT interval range that we will be using as a reference is  $435.9\text{ ms} \pm 4.7$ . This is based on a study of third trimester pregnant parturients (10).

All ECGs will be recorded in duplicate at a paper speed of 50mm/s. Each trace will be allocated a three-digit random number code to allow

*Figure 1(15): 12 lead Electrocardiogram (ECG) electrode placements in standard locations-a) pre-cordial electrodes and placement, b) Limb electrodes and placement.*

Identification of pre and intra-operative traces after analysis. Automated measurements, patient identifiers and times will be removed from the traces prior to analysis by study investigators. The anesthetic will be standardized for all patients. All patients will receive a Ranitidine 50mg IV infusion as a standard premedication.

After arrival in the operating room the patient will receive spinal anesthesia by single shot technique in the sitting position using a standardized dose consisting of hyperbaric 0.75% bupivacaine 12mg, 10mcg fentanyl and epidural preservative free morphine 100mcg. After the application of the spinal anesthesia, the patient is positioned in a left-lateral tilted recumbent position to avoid aorto-caval compression. A fluid pre-load using 0.9% normal saline or plasmalyte is infused while the patient is monitored with standard monitors including pulse oximeter, electrocardiogram and non-invasive blood pressure cuff around the upper arm. Each participant will receive an infusion of phenylephrine started after induction of spinal anesthesia at 50mcg/min to maintain BP at 100% of baseline. They will also receive Cefazolin IV 2g for surgical antibiotic prophylaxis.

An intra-operative 12 lead ECG, using the same electrode positions (figure 1) will be taken 5 minutes after induction of spinal anesthesia in the left lateral tilted position. Following delivery of the fetus and cord clamping, each patient will receive a bolus of carbetocin, 50mcg or 100mcg diluted in a 10mL normal saline syringe administered through a pump to be given over 1 min. The attending anesthesiologist will prepare the randomized carbetocin study dose and will not be involved in any other aspects of the study.

Further 12 lead ECGs will be acquired using the same electrode positions (figure 1) at 5 and 10 minutes after giving the study drug. Based on anecdotal clinical experience, the ECGs acquired at these time intervals do not interfere with any family or maternal-fetal bonding. The patient's involvement in the study will then be complete and the conduct of anesthesia continued at the discretion of the supervising anesthetist. Anti-emetics prophylaxis will be given after the final ECG recording, ondansetron 4mg and dexamethasone 5mg.

A postoperative 12 Lead ECG will be taken for safety purposes but will not be used for analysis. This postoperative ECG will be examined by the attending anesthesiologist and patients will be monitored in

the postanesthetic care unit (PACU) for up to 2 hours. If any abnormalities were found, an obstetric internal medicine specialist will be consulted.

All ECGs will be recoded in duplicate, at a paper speed of 50mm/sec and amplification of 0.1mV/mm and with no identifying data including time or automated analysis on the recorded traces. Each ECG will be given a random three-figure code to allow identification of the paired pre and intra-operative traces after analysis.

In case of insufficient uterine tone, the patient will be treated according to the current standard of care. Other options for ongoing care in case of uterine atony include uterine massage, ergometrine, oxytocin infusion, misoprostol, hemabate or Bakri balloon insertion. The choice of one or several of these interventions is according to severity of uterine tone and at the discretion of the obstetrician. In the event of any of these interventions occurring prior to the 10-minute ECG recording, the patients will be withdrawn from the study.

A summary of the protocol is shown in the flow diagram (Figure 2).

[figure not shown]

Figure 2: Study Flow Diagram. Abbreviations: Electrocardiogram (ECG), blood pressure (BP), heart rate (HR), Oxygen saturations (SpO2).

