**Sample size:**

The primary outcomes of our study are changes in Tp-e at 5 min post carbetocin administration compared to baseline for carbetocin 50mcg and carbetocin 100mcg. The published data(11) for the mean change in Tp-e for oxytocin at 5 min for pregnant patients undergoing spinal anesthesia for Cesarean delivery is 12ms with a standard deviation (SD) of 7. Using paired t-test, type I error of 0.05 and 99% power, 9 patients per group would be required. To adjust for two separate primary outcomes for 2 separate doses, an alpha correction factor of 2 is applied (i.e., 0.025), and assuming a wider SD for carbetocin of 10, 17 per group is needed. To account for attrition a total of 50 patients (25 per group) will be recruited.

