**Data analysis:**

The QT and Tp-e intervals will be measured for all complete P-QRS-T cycles in lead II and V5 and averaged to give a mean QT interval and Tp-e interval for that lead. The QT interval will be measured from the start of the QRS complex to the end of the T-wave, defined as the point of return to the T-P baseline. If U waves are present, the end of the T-wave will be taken as the nadir of the curve between the T-wave and U waves. The Tp-e interval will be measured from the peak of the T-wave to the end of the T-wave. Monophasic T-wave peaks can be identified visually. For more complex T-wave morphologies, the peak will be identified according to the criteria Emori & Antzelevitch(16).

Within-group and between-group comparisons of pre and post carbetocin ECG indices will be performed using two-way analysis of variance.

ECGs will be interpreted by [name] MD, cardiology fellow at the University of British Columbia, and a PhD student at the University of Alberta. If an abnormality is identified at the time of ECG analysis, the patient will be contacted and an internal medicine specialist and a cardiologist will be consulted if deemed necessary.

Normal values for QTc and Tp-e in pregnancy will be used from a study by Tanindi et al(10).

	Nonpregnant (n = 62)	First Trimester (n = 41)	Second Trimester (n = 45)	Third Trimester (n = 68)	P
Pmax	93.0 ± 9.1	93.9 ± 8.9	97.9 ± 5.6	99.0 ± 6.1	<0.001*
Pmin	62.4 ± 8.2	62.9 ± 6.8	64.4 ± 5.1	64.1 ± 4.9	0.83
QTc max (Bazett's)	425.98 ± 14.7	425.9 ± 15.05	428.5 ± 12.9	435.9 ± 4.7	<0.001†
QTc min (Bazett's)	397.7 ± 14.1	397.2 ± 14.1	399.9 ± 12.6	402.5 ± 4.7	0.19
QTc peak (Bazett's)	331.4 ± 13.1	333.1 ± 12.8	332.7 ± 11.9	335.6 ± 15.3	0.31
QTc max (Fridericia)	407.4 ± 14.2	408.5 ± 16.1	410.1 ± 13.1	415.1 ± 10.1	0.007‡
QTc min (Fridericia)	380.5 ± 13.7	381.1 ± 15.2	381.7 ± 13.7	383.6 ± 9.7	0.55
QTc peak (Fridericia)	315.1 ± 16.3	317.5 ± 11.6	317.2 ± 16.4	320.7 ± 16.6	0.25
Tp-e	72.7 ± 6.2	73.2 ± 6.5	77.2 ± 8.9	87.2 ± 9.6	<0.001†
Tp-e/QT	0.17 (0.14–0.20)	0.17 (0.14–0.20)	0.18 (0.15–0.23)	0.20 (0.16–0.25)	<0.001†

P < 0.05 is considered as statistically significant. For the comparisons where Bonferroni's correction was applied, P < 0.008 is considered as statistically significant.

\*Significant difference is between nonpregnant group-second trimester, nonpregnant group-third trimester, first trimester-third trimester.

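### The baseline ECG withdrawal rule uses 435.9 ± 4.7 ms as a QT range, but that figure is a group summary of maximum Bazett QTc, not an upper limit of normal

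*Protocol*

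**What the plan says.** The Protocol, Interventions (Study Protocol), has the study team read each woman's baseline ECG in the preoperative area. The rule is: "If the QT interval is prolonged on the baseline ECG, the patient will be withdrawn from the study". A referral to obstetric internal medicine follows. The yardstick is introduced with "The QT interval range that we will be using as a reference is", followed by 435.9 ms ± 4.7 and a citation to a study of women in the third trimester.

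Three other places bear on how to read that figure:

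- Data analysis says "Normal values for QTc and Tp-e in pregnancy will be used from a study", which is the same cited study, and reproduces its table. The table gives QTc by both Bazett and Fridericia, and as maximum, minimum and peak values.
- Data analysis also says "The QT and Tp-e intervals will be measured for all complete P-QRS-T cycles in lead II and V5". This concerns the study measurements, not the preoperative screen.
- Background reports from the same study that QTc, Tp-e and their ratio "were all increased in the third trimester of pregnancy but were still within the normal range of non-pregnant women".

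The SAP does not mention the screen. Neither document names the QTc correction formula that the trial will use.

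**The concern.** A withdrawal rule of this kind needs three things: a defined measure, a way of obtaining it, and a value above which the woman is withdrawn. The text supplies a number that fits none of these roles. It is labelled QT but comes from a QTc row. It is called a range but is a group value ± spread. It is offered as the reference for prolongation although the Background describes such values as normal.

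The wording can be applied in ways that give very different results. Taken as a Bazett limit, it would send a noticeable share of ordinary women to a specialist shortly before surgery and remove them from the trial. Taken literally as raw QT, it would let through women whose corrected interval is clearly long. This is the only ECG check before the study drug is given, and the trial exists because that drug is suspected of prolonging repolarization.

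**Working it through.** **Step 1: trace the figure.** In the table under Data analysis, 435.9 ± 4.7 appears in one cell only: third trimester (n = 68), QTc max by Bazett. The match is exact, so the source is certain. The same column gives QTc max by Fridericia as 415.1 ± 10.1 and QTc min by Bazett as 402.5 ± 4.7.

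**Step 2: what the band means.** 435.9 − 4.7 = 431.2 ms and 435.9 + 4.7 = 440.6 ms. If ± is an SD (the reproduced table does not label it) and values are normal, this band holds about 68% of ordinary third-trimester women.

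**Step 3: share of ordinary women above 440.6 ms.** The rule does not state this limit; the upper edge is used here as one plausible reading. Share = P(Z > (440.6 − mean)/SD); the last column is 50 × share.

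| Measure | Mean | SD | z | Share | Of 50 |
|---|---|---|---|---|---|
| Bazett QTc max, printed SD | 435.9 | 4.7 | 1.00 | 15.9% | 7.9 |
| Bazett QTc max, SD from the Fridericia max row, same women | 435.9 | 10.1 | 0.465 | 32.1% | 16.0 |
| Bazett QTc max, second-trimester SD | 435.9 | 12.9 | 0.364 | 35.8% | 17.9 |
| Bazett QTc max, first-trimester SD | 435.9 | 15.05 | 0.312 | 37.7% | 18.9 |
| Fridericia QTc max | 415.1 | 10.1 | 2.52 | 0.6% | 0.3 |

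The choice of cut-off matters as much. With Bazett QTc max and SD 4.7, the share flagged is 50% at the mean (435.9), 15.9% at mean + 1 SD (440.6) and 2.3% at mean + 2 SD (445.3).

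**Step 4: effect of lead.** The table does not define its maximum. If it is the longest value across leads, a single-lead value such as II or V5 would lie between the minimum and maximum means. Take the midpoint as an assumption: (402.5 + 435.9)/2 = 419.2 ms. The share above 440.6 ms is then about 0% at SD 4.7, 1.7% at 10.1, 4.9% at 12.9 and 7.8% at 15.05.

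**Step 5: literal reading as raw QT.** Bazett divides QT by RR^(1/2) and Fridericia by RR^(1/3), so the ratio of the two is RR^(−1/6). From the table, RR = (435.9/415.1)^(−6) = 0.746 s, or 60/0.746 ≈ 80 bpm. A raw QT of 440.6 ms at that rate is a Bazett QTc of 440.6/√0.746 ≈ 510 ms. The QTc min row gives nearly the same: (402.5/383.6)^(−6) = 0.749 s and 509 ms.

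**Step 6: effect on the primary analysis.** The Protocol's Sample size section says "a total of 50 patients (25 per group) will be recruited" and needs 17 per group; the SAP needs 16. At the printed SD, 25 × (1 − 0.159) ≈ 21 per group remain. At the widest borrowed SD, 25 × (1 − 0.377) ≈ 16 remain. Exact paired t-test power (noncentral t, effect 12/10, two-sided alpha 0.025) is 98.4% at 16, 98.9% at 17 and 99.8% at 21.

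**The case against.** The strongest reply is that the figure is only a reference. The rule leaves prolongation to the study team, and no sentence withdraws women above 440.6 ms. That is correct, and it means every count in Step 3 illustrates a possible reading and does not predict losses. It does not rescue the text, because the one number the team is given is the wrong kind of number.

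Second, the formula can be worked out: the figure matches one cell, and that cell is labelled Bazett. This also stands, and it makes the raw-QT reading unlikely to be the intent. But the reader has to find the match in a later section, and having found it still has no cut-off or lead.

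Third, 4.7 is the printed spread, and the wider SDs belong to other women or another formula. This is fair. The shares of 32% to 38% are a sensitivity range only. The 4.7 looks small beside the rest of its row (12.9 to 15.05), but the Bazett minimum in the same women also carries 4.7, and the source cannot be checked here.

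Fourth, a sponsor may choose a cautious limit on purpose. Values within the normal range do not logically rule that out. If caution was the aim, the text should say so and give the limit.

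Fifth, the safety stakes are bounded. The Background says carbetocin at these doses is routine at this hospital and first line even for women with long QT syndrome. A woman missed by the screen would probably receive the same drug outside the trial; what she loses is the specialist review before surgery. The history exclusions, the postoperative ECG and the specialist follow-up of abnormal traces described under Data analysis remain as partial safeguards, though both ECG safeguards act after dosing.

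**Conclusion.** The point holds, and it should be fixed. What is certain is that the reference is mislabelled as QT, is a group summary of maximum Bazett QTc, and is not an upper limit of normal, and that the screen has no stated cut-off or lead.

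The size is conditional. With normal values, ± as an SD and a limit of 440.6 ms, about 16% of ordinary women are flagged on maximum Bazett QTc. The share is higher if the true spread is wider, 0.6% by maximum Fridericia QTc, and possibly small if a single lead is used.

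A reader might infer three stronger conclusions that the documents do not support:

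- *The trial would lose a third or more of its women and become underpowered.* This needs an inferred cut-off, the maximum QTc and a borrowed SD all together, and even then power is about 98% at 16 per group.
- *The Tp-e result would be biased.* The screen uses an ECG taken before the study drug, so the dose cannot influence who is withdrawn.
- *Withdrawal falls after the allocation is known.* The text says "enrolled patients will be randomized to one of two groups" before it describes the baseline ECG. It does not say when the envelope is opened, and the flow diagram was not available to this review. That is a separate, unproven matter, and no change is proposed for it here.

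The consequence is therefore misapplied safety screening, needless referral and avoidable losses, not a threat to the primary comparison.

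**What to change.** In the Protocol, Interventions (Study Protocol), replace the 435.9 ± 4.7 QT reference with a QTc criterion that states:

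- one correction formula;
- the lead or leads to be read (for example II and V5, which are already measured for the outcomes);
- one explicit upper limit of normal for that measure, chosen by the sponsor's cardiology advisers, and not a mean ± SD band.

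The cost is a short wording change and one decision by the sponsor on formula and limit. It needs no new data, visits or staff.
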